Name : _____	 antiemetic  antidiarrhoeal  anti-neutropenic  antihypertensive  mouthwashes and local anaesthetics  emollients, moisturising creams  analgesics  anti-gastro-oesophageal reflux agents  bisphosphonates  Other, specify _____	 Date first taken: _____ / _____ / _____ (DD/MM/YYY)  when necessary	 Ongoing  Stopped, End date _____ / _____ / _____ (DD/MM/YYY)	 Curative  Preventive  Not available	 Dosage regimen: _____ doses _____ time(s) per day for _____ weeks  Not available	Recommendations: _____  Not available

Instruction: identifying all treatments available to the patient will allow the nurses to adapt the advice and actions to be implemented. The nurses will have received an anonymised copy of the patient's prescriptions from the physician

D.2.2.2. Introduction to the mid-cycle interviews (excluding the first call of the cycles)

- 4- **If mid-cycle call:** Let's go over the treatments prescribed by your physician. During our last call, you stated that you had a number of support prescriptions or treatments for managing adverse events. Have you been prescribed any additional treatments since last time? Yes No
- If Yes, Do you have the prescriptions with you? Do you know what medicines have been prescribed for you?*
 - (record all new prescriptions)*

Table 2 + Concomitant treatments						
Surname	Indication	Date first taken	Status	Reason for prescription	Dosing	Physician's advice
Overview of previous treatments						
Name : _____	 antiemetic  antidiarrhoeal  anti-neutropenic  antihypertensive  mouthwashes and local anaesthetics  emollients, moisturising creams  analgesics  anti-gastro-oesophageal reflux agents  bisphosphonates  Other, specify	 Date first taken: _____ / _____ / _____ (DD/MM/YYY)  when necessary	 Ongoing  Stopped, End date _____ / _____ / _____ (DD/MM/YYY)  Not available	 Curative  Preventive  Not available	 Dosage regimen: _____ doses _____ time(s) per day for _____ weeks  Not available	Recommendations: _____  Not available

Instruction: identifying all treatments available to the patient will allow the nurses to adapt the advice and actions to be implemented. The nurses will have received an anonymised copy of the patient's prescriptions from the physician

D.2.3. "Freephone" interview

Instruction: During calls to the freephone number, the nurse can access all of the CATI questionnaire in order to meet the patient's request. Once the patient's request has been dealt with, either the next interview can be conducted, depending on its theoretical date, or an appointment can be made

- What is the reason for your call?
 - Answer, Advice, Action *[Provide the appropriate answer to the question, by reference to the concerned section of the questionnaire]*
- Do you have any other questions or problems you would like to discuss?
 - If yes, *[Go to q1]*
 - If no, *[Go to q3]*

- 3- We had agreed to call you on [date] to go over your health and treatment management in greater detail. Would you like to talk about this now?

- *If yes, [redirection to "Regular" questionnaire]*
- *If no, Could we make an appointment for this interview? [Make an appointment]*

D.3.Compliance and care pathway

If 1st call The rest of the discussion covers the period from the last appointment with your oncologist dated [inclusion date] (*Sutent® initiation consultation*) to the current date.

If subsequent calls: The rest of the discussion covers the period from the last call, dated [date of last call] to the current date.

D.3.1. Treatment compliance

Since our last call, have you taken your treatment every day?

Yes No

- a) **If yes,** For information, if you forget to take your capsule one day, do not attempt to make up for this omission by taking 2 capsules the next day, take only the usual dose.

If W4 calls for Cycles 1, 2 or 4: Morisky treatment compliance questionnaire

The following questions concern the entire current cycle, hence the past 4 weeks:

- i. Did you, at any time, forget to take your treatment? Yes No
- ii. Did you sometimes have trouble remembering to take your treatment? Yes No
- iii. Did you ever stop taking your treatment when feeling better? Yes No
- iv. If you felt worse when taking your treatment, did you at any time stop taking it? Yes No
- v. When you suffered an adverse event, did you ever reduce or adapt the treatment? Yes No

→ *If at least 1 Yes:* Have you forgotten or interrupted your treatment since our last call?

- b) **If No,** could you describe to me the periods when you did not take your treatment? What was the reason? *[Report the interruption - Table 3]*

↳ *If omission:* For information, if you forget to take your capsule one day, do not attempt to make up for this omission by taking 2 capsules the next day, take only the usual dose.

- *If W4 calls for Cycles 1, 2 or 4: Morisky treatment compliance questionnaire.*

The following questions concern the entire current cycle, hence the past 4 weeks: *[qualify the question if the patient declared having forgotten or interrupted his/her treatment: "We have already discussed this, but I need to validate certain details"]*

- i. Did you, at any time, forget to take your treatment? Yes No
- ii. Did you sometimes have trouble remembering to take your treatment? Yes No
- iii. Did you ever stop taking your treatment when feeling better? Yes No

- iv. If you felt worse when taking your treatment, did you at any time stop taking it? Yes No
- v. When you suffered an adverse event, did you ever reduce or adapt the treatment? Yes No

Table 3 - Treatment interruptions

Date	Duration (days)	Reason for interruption
Overview of previous interruptions		-
__ / __ / __ (DD/MM/YYYY)	Ongoing	Adverse event Medical decision Omission Lack of efficacy Improved health Other:

Instruction: if Adverse event is ticked, the AE declaration table appears for data input. New AEs are added to the table in section D.5. AE collection

D.3.2. Scheduled and unscheduled medical procedures

- ↳ Have you called upon or consulted a healthcare professional since our previous interview (or since the start of treatment for the first call)? Yes No
- *If new call, [Report a new call – Table 4]*
 - *If new consultation, [Report a new consultation – Table 4']*
- ↳ *If cycle-end call (week 4):* Are you scheduled to see your oncologist during the coming weeks? Yes No
- *If yes, [Report a new consultation]*
 - *Reminder:* Before the consultation with your oncologist, do not forget to perform all the additional tests he/she asked for, to help him/her define the most appropriate treatment. If you have a follow-up notebook in which you take notes, remember to bring it with you.

Table 4 - History of calls to a healthcare professional

Date	Type of call	Specialist field of the healthcare professional	Reason for the call	Action implemented
Overview of previous calls				
__ / __ / __ __ __ __ (DD/MM/YYYY)	 Scheduled  Unscheduled	List {General practitioner; Oncologist; Cardiologist; Nephrologist; Accident and Emergency; Nurse; Other, etc.} If Other, specify: _____	 AE; specify: _____  Other	 Temporary Sutent® interruption  Treatment prescribed Specify: _____  Consultation with medical specialist  Nephrologist  Cardiologist  Other: _____  Consultation with attending physician  Emergency department. Date: __ / __ / __ (DD/MM/YYYY) Location: _____ Hospitalisation:  Yes  No  Hospitalisation. Date: __ / __ / __ (DD/MM/YYYY)

				Location: _____  Hygiene and nutrition advice  Other, specify: _____  Not applicable
--	--	--	--	---

Instruction: if Adverse event is ticked, the AE declaration table appears for data input. New AEs are added to the table in section D.5. AE collection

Table 4' - History of consultations with a healthcare professional

Date	Type of consultation	Specialist field of the healthcare professional	Reason for consultation	Action implemented
Overview of previous consultations				
____/____/ ____/____/ (DD/MM/YYYY)	 Scheduled  Unscheduled	List {General practitioner; Oncologist; Cardiologist; Nephrologist; Accident and Emergency; Nurse; Other, etc.} If Other, specify: _____	 AE; If yes, specify which one: _____  Scheduled examination  Other	 Sutent® dose modification  Temporary Sutent® interruption  Termination of Sutent®  Treatment prescribed Specify: _____  Consultation with medical specialist  Nephrologist  Cardiologist  Other: _____  Consultation with attending physician  Emergency department. Date: ____/____/____ (DD/MM/YYYY) Location: _____ Hospitalisation:  Yes  No  Hospitalisation. Date: ____/____/____ (DD/MM/YYYY) Location: _____  Hygiene and nutrition advice  Other, specify: _____  Not applicable

Instruction: if Adverse event is ticked, the AE declaration table appears for data input. New AEs are added to the table in section D.5. AE collection

D.3.3. Hospitalisations or visits to accident and emergency

- ↘ Have you been hospitalised, or have you been to accident and emergency since our previous interview (or since the start of treatment for the first call)? Yes No
 - *If Yes, [Report a new hospitalisation – Table 5]*
 - *If Yes, Did the hospitalisation lead to a temporary interruption of treatment?? Yes No*
 - *If Yes, have we discussed this previously? Yes No*
 - *If No, [Report a new treatment interruption – Table 3]*

Table 5 - Hospitalisations or visits to accident and emergency

Date	Type of hospitalisation	Duration (days)	Location	Reason	Action implemented
Overview of previous hospitalisations					
/ / (DD/MM/YYYY)	 Scheduled  Unscheduled	 day  Not available	 Day hospital  Hospital / University Hospital  CLCC  Private clinic  Other: _____  Hospital (no details)	Adverse event Other: _____	 Sutent® dose modification  Temporary Sutent® interruption  Termination of Sutent®  Treatment prescribed Specify: _____  Consultation with medical specialist  Nephrologist  Cardiologist  Other: _____  Consultation with attending physician  Emergency department. Date: / / (DD/MM/YYYY) Location: _____ Hospitalisation:  Yes  No  Hospitalisation. Date: / / (DD/MM/YYYY) Location: _____  Other, specify: _____  Hygiene and nutrition advice  Not applicable

Instruction: if Adverse event is ticked, the AE declaration table appears for data input. New AEs are added to the table in section D.5. AE collection

D.3.4. Monitoring additional examinations

↳ **If cycle-start call for cycle 1, 2, 3 or 4 (post oncologist visit)**

Did your oncologist ask you to perform additional examinations over the coming weeks of treatment? Yes No

- *If Yes, What examinations did he/she recommend carrying out? When do you need to do them? [\[Add an examination – Table 6\]](#)*

↳ *If you have these examinations before the next call, do not hesitate to have your results with you so we can discuss them.*

- *Amongst these examinations, have you already had any? Which ones?*
 - *If Yes, Are there any points you would like to talk about? [\[AE report depending on results\]](#)*

↳ **If mid-cycle call:**

↳ During our previous calls, you stated having one or more additional examinations. Did you do them? Yes No

- *If Yes, When did you have it? [\[update Table 6\]](#)*

○ *If Yes, Are there any points you would like to talk about? [\[AE report depending on results\]](#)*

- *If No, The examination results that you notify to the medical team in charge of following you may, if your physician deems necessary, lead to an adaptation of your treatment. It is thus important that you undergo the examinations requested by your physician in order to help him/her care for you.*

Table 6 - Additional examinations

Type of examination	Recommended date	Status	Result
Biological examination, blood sample	 Date: ___/___/___ (DD/MM/YYYY)  Frequency: ___/wk  Not applicable	 Done, date: ___/___/___ (DD/MM/YYYY)  Appointment made, Date: ___/___/___ (DD/MM/YYYY)  To do	 Don't know  Normal  Abnormal: AE
Urine analysis			
Hypertension monitoring			
Cardiovascular profile			
Thyroid function profile			
Liver profile			
Oral profile			
Skin clinical examination			
Other:			

D.4. Tolerance and actions implemented

Monitoring of the outcome of previously reported adverse events

- During the last call of [\[date\]](#), we spoke of your problems concerning [\[event\]](#).
 - What is the current situation? [\[Update Table 7\]](#)
 - We had determined that you could do [\[action\]](#) to prevent / relieve [\[event\]](#). Did you do it? Did it provide relief? [\[Update Table 7\]](#)

↳ Adverse event follow-up

- If the AE is resolved and where applicable, inform the patient of actions to implement to prevent the recurrence of symptoms
- In the event of AE progression, new estimation of grade and of medical actions to implement [\[see section D.5. New AE collection\]](#)

Table 7 - Adverse events (past and current)

Type of event	Description of the event	Start date	Severity	Grade (CTCAE v4.03)	Impact on activities of daily living	Causal relationship	Change	Corrective medical action	Action on suspected treatment
Overview of all previous AEs (e-CRF + CATI) and follow-ups									
(list choice)	--/--/(DD/MM/YYYY)	 Non-serious  Serious If serious, severity criteria (several possible answers):  Caused death If death, specify: Date of death: --/--/(DD/MM/YYYY) Cause of death: ___  Life-threatening  Hospitalization / prolonged hospitalization  Permanent or major invalidity or disability  Anomaly / congenital malformation  Medically significant event	 Grade 0  Grade 1  Grade 2  Grade 3  Grade 4	 Does not affect daily life  Makes certain actions difficult to accomplish  Affect activities of daily life	 Related to taking Sutent®  Related to a concomitant medicine; Specify the treatment: ___	 Recovered If recovered, recovery date: --/--/(DD/MM/YYYY)  Recovered with sequelae If recovered, recovery date: --/--/(DD/MM/YYYY)  Recovering  Not recovered  Unknown	 Prescription of a treatment, specify:  Medical consultation (general practitioner, specialist, emergency department)  Hospitalisation.  Nurse's advice, specify: ___  Other, specify: ___  Not	 Interruption (temporary, permanent, or delayed)  Dose reduction  Dose increase  Dose unchanged  Unknown  Not applicable

							applicable	
--	--	--	--	--	--	--	------------	--

Instruction: for all current AEs, check AE outcome. If the AE is unresolved, a new row will be generated and linked to the source row. AEs reported by the physicians via the e-CRF are distinguished from AEs reported by the nurses using CATI.

D.5. New AE collection

Intro: as the interview progresses the nurse will gain access to the various screens concerning the adverse events described by the patient at any time during the telephone conversation; moreover, at this stage of the interview, the nurse will check for any other AEs that may not have been mentioned before.

Since the last interview, since starting taking Sutent® (for the first call), have you had any discomfort, or have you experienced unexpected effects related to your Sutent® treatment other than those we have already discussed? Yes No

- If Yes, [\[Go to AE information collection questionnaire\]](#)
 - ↳ Once the patient has finished describing the AE: Have you experienced any other discomfort or adverse reactions?
- If not, check for the absence of AEs: Do not hesitate to report any problems you might encounter, even the mildest such as for example:
 - Changes to skin, nail or hair
 - Digestive disorders
 - Breathing difficulties
 - Heart disorders or change in blood pressure
 - Mouth or gum problems
 - Other adverse events such as tiredness or fever, etc.

Ongoing grade 3 / 4 AE: Recommendation for temporary interruption of Sutent® treatment pending oncologist's medical opinion: Yes No

- ↳ If Yes, In this situation, I recommend that you temporarily interrupt your Sutent® treatment until further notice. Your oncologist will be alerted and his/her medical opinion requested. We will contact you to inform you of his/her decision.

Activities of daily life: preparing meals, shopping, using a telephone, paying.

Major daily activity: Showering, dressing and undressing, eating, going to the toilet.

Instruction: any report of a grade 3 or 4 AE, except for a biological AE, will trigger an email alert for the oncologist + Level 3 TEC. Other alerts are generated on a case by case basis for certain grade 2 AEs.

Table 8 - AE / Grade / Action look-up table for Sutent®-related AEs

Adverse event	CTCAE grade estimation	Recommendations and Actions to implement
Skin toxicity		

 - Skin irritation - Dry skin - Cracked skin - Nail fissures - Hyperkeratosis (corn, psoriasis, warts) 	
 - Intensity of dryness? 
 o Asymptomatic <10% of body area and not associated with erythema or pruritus (Grade 1) o Symptomatic 10 to 30 % of body area and associated with erythema or pruritus (Grade 2) o >30% of body area and associated with erythema or pruritus (Grade 3) - Impact on daily life 
 o Does not affect activities of daily life (Grade 1 / 2) o Affects activities of daily life (Grade 2 > Grade 3) 	
 - No event / prevention: moisturising cream to prevent dryness, Dexeryl or Biafine emollient cream, pedicure and manicure at start of treatment - Grade 1: antiseptic foot bath, bepanthren / moisturising cream for relief, salicylic acid officinal formula (apply a thick layer of cream after evening ablutions, then put on socks). Use gentle and scent-free soap. - Grades 2 and 3: consultation with dermatologist or chiropodist (rapid care required as difficult to estimate / manage over the phone)

 - Hand and foot syndrome 	
 - Minor skin 
 o Alterations or dermatitis (Grade 1) o Desquamation, blisters, haemorrhagic lesions, oedema (Grade 2) o Ulcerative lesions (Grade 3) - Sensitivity / pain / discomfort 
 o Painless (Grade 1) o Pain with no functional impairment (Grade 2) o Functional impairment with no pain (Grade 2) 	
 - Grade 1: urea-based daily use keratolytic emollients, e.g.: Xerial® 30 or 50 (labo SVR), Akerat S® (Avène). - Grade 2: consultation with oncologist or GP if involved in patient follow-up and good relationship with patient + alert oncologist in report. - Grade 3: patient's condition requires consultation with oncologist

	
 ○ Pain and functional impairment (Grade 3) 	

 - Skin colouration - Dermal alteration 	
 - Intensity of discolouration 
 ○ Mild: < 10% of body area → No psychological impact. (Grade 1) ○ Pronounced: >10% of body area + psychological impact (Grade 2) - Dermal alteration 
 ○ Mild thickening (Grade 1) ○ Leathery appearance; papillary formation (Grade 2) 	
 - No event / prevention to grade 2: temporary non-contagious alteration, without consequences. No direct care required.

 - Alopecia 	
 - Intensity of hair loss 
 ○ Thinning or localised <50%, wig not needed. (Grade 1) ○ Total (Grade 2) 	
 - Grades 1 and 2: no treatment or action to implement, but reversible in most cases
Digestive disorders		

 - Acid reflux - Heartburn 	
 - Description of intensity 
 ○ Mild (Grade 1) ○ Moderate or mild, but frequent (Grade 2) ○ Severe or moderate, but frequent (Grade 3) 	
 - Grade 1: Gaviscon for initial reflux episodes. Avoid food causing reflux - Grade 2: continue Gaviscon + Inexium (IPP) as self-medication if reflux too frequent - Grade 3: contact oncologist

 - Diarrhoea 	
 - stool frequency 
 ○ stools more frequent, but < 4/day compared to usual, not necessarily liquid (grade 1) ○ very frequent stools < 4-6/day, liquid (grade 2) ○ >7 stools/day, incontinence, impact on activities of daily living. - Accompanied by vomiting? 
 ○ Yes (Grade 3) 	
 - Grade 1: Dietary advice (drink often and in small amounts; low-fibre diet) + take antidiarrhoeal agents prescribed by physician: smecta, the imodium, then tiofan according to intensity (reassess the grade) - Grade 2: if treatments no longer sufficient, contact attending physician. - Grade 3: vomiting + diarrhoea: consult GP rapidly as need to be examined

 - Nausea - Vomiting 	
 - Nausea: 
 ○ loss of appetite with no change in eating 	
 - Grade 1: antinauseant / preventive anti-emetic; nutritional advice (eat slowly, fractionate meals,

	
 habits (Grade 1) ○ Reduction in food intake, without significant weight loss, dehydration or malnutrition. (Grade 2) ○ Reduced calorie intake or tube feeding (Grade 3) 
Vomiting:
 
 - Frequency / 24 hours 
 ○ 1 to 2 episodes (at least 5 min. apart). (Grade 1) ○ 3 to 5 episodes (at least 5 min. apart) (Grade 2) ○ >6 episodes, reduced calorie intake or tube feeding - Other factors? 
 ○ Persistence over 48h or combined with diarrhoea (Grade 1 → 2, 2 → 3) 	
 - avoid fatty or spicy meals, drink between meals) - Grade 2, 3: persistent or vomiting + diarrhoea: consult GP rapidly as need to be examined 	
- Abdominal pain	
 - Pain level 
 ○ Mild (Grade 1) ○ Moderate + impact on activities of daily living. (Grade 2) Severe ++ major impact on activities of daily living (Grade 3) - Blood in stools (Grade 2 > 3) 	
 - Grade 2: alert oncologist in report - Grade 3: contact oncologist by phone + alert oncologist by email 	
Heart disorders			
- Hypertension	
 - Have you measured your blood pressure, or had it measured recently? 
 ○ 120-139 / 80-89 (Grade 1) ○ 140-159 / 90-99 (Grade 2) ○ ≥ 160 / ≥100 (Grade 3) ○ Malignant HTN, transient or permanent neurological deficit (Grade 4) 	
 - Grade 1: Continue regular monitoring and taking treatment if prescribed. Contact oncologist preventively as nurse does not have all necessary information to determine severity - Grades 2 and 3: Contact oncologist rapidly, he/she will decide whether treatment should be initiated 	

	
 - Other concomitant symptoms? 
 o Dizziness, tiredness (Grade 1 > Grade 2) o Pre-existing heart disease, kidney failure, single kidney (Grade 1> Grade 2, Grade 2 > Grade 3) 	
Haemorrhagic and endocrine disorders		
- Anaemia	
 - STANDARD Man: 13 – 17 g/dL; Woman: 12 – 15 g/dL - Grade 1: < 10 g/dL (6.2 mmol/L or 100g/L) - Grade 2: 8 – 10 g/dL (6.2- 4.9 mmol/l or 100-80g/L) - Grade 3: <8 g/dL (\leq 4.9 mmol/L or 80 g/L) 	
 - Grade 1: no action - Grade 2: oncologist email alert - Grade 3: patient contacts oncologist
- Haematuria		
 - Alert oncologist by email as soon as haematuria observed
- Neutropenia	
 - Grade 0: 1,8 – 7 *10⁹/L - Grade 1: 1,5 – 1,8 *10⁹/L - Grade 2: 1,0 – 1,5 *10⁹/L - Grade 3: 0,5 – 1,0 *10⁹/L (1000 mm³ + fever) - Grade 4: <0,5 *10⁹/L 
Presence of fever? Yes (Grade 2 > 3, 3 > 4)
	
 - Grade 1: no prescription of GCSF, talk to oncologist at next visit - Grade 2: alert oncologist in report - Grade 3: alert oncologist by email; if fever: Fever management advice + rapidly contact oncologist by phone - Grade 4: rapidly contact oncologist by phone
- Thrombocytopenia	
 - STANDARD > 150 * 10⁹/L - Grade 1: 75,0 – 150 *10⁹/L - Grade 2: 50,0 – 75,0 *10⁹/L - Grade 3: 25,0 – 50,0 *10⁹/L 	
 - Grade 1: no action recommended - Grade 2: oncologist email alert - Grade 3: rapidly contact oncologist + alert oncologist by email
- Increased creatininaemia	
 - STANDARD: 7 to 13 mg/L - Grade 1: 1 to 1.5* previous value - Grade 2: 1.5 to 3* previous value - Grade 3: 3 to 6* previous value - Grade 4: >10 * previous value 	
 - No grade 1 event, recommend drinking to avoid dehydration. Creatinine drops during the 2 weeks of break. - Grade 2: oncologist email alert - Grade 3: rapidly contact oncologist + alert

	
 - 	oncologist by email
- Hypothyroidism	
 - Grade 1: TSH 5 to 10 µU/mL - Grade 2: TSG > 10 µU/mL 	
 - Grade 1: asymptomatic, does not require management - Grade 2: general practitioner, additional tests to implement appropriate treatment
- Hyperthyroidism	
 - Grade 1: TSH 0.30 to 0.10 µU/mL - Grade 2: TSH < 0.10 µU/mL 	
 - Grade 1: asymptomatic, does not require management - Grade 2: general practitioner, additional tests to implement appropriate treatment
Infectious problems		
- Mucositis - Stomatitis - Ulcers - Infections of the oral mucosa	
 - Intensity and location 
 o Asymptomatic (Grade 1) o Localised ulceration, swallowing difficulties, dry mouth (Grade 2) o Confluent ulcers, mild bleeding (Grade 3) o Tissue necrosis, significant spontaneous bleeding (Grade 4) - Diffuse pain? (Grade 2) 	
 - No grade 2 event: systematic treatment by sodium bicarbonate mouth wash + Kéal; oral hygiene advice (regular tooth brushing with a soft toothbrush) 
 o If ulcers present, fungal treatment and/or viscous xylocaine treatment o If pain, Efferalgan® codeine mouthwash - Grade 3: Contact oncologist / emergency department rapidly - Grade 4: Emergency department / hospitalisation
- Gingivitis	
 - How intense is the pain? 
 o Mild (Grade 1) o Moderate (Grade 2): o Severe (Grade 3) - Do you experience discomfort when eating meals? 
 o Mild (Grade 1) o Strong discomfort with oral meals (Grade 2) o Oral feeding impossible (Grade 3) - Diffuse pain? (Grade 2) 	
 - Grade 1: treatment with pansoral, talk to oncologist at next visit - Grade 2: efferalgan codeine mouthwash for pain. Talk to oncologist at next visit. Alert oncologist by email. - Grade 3: Alert oncologist by email + call oncologist
- Diffuse oral pain	
 o - Moderate pain (Grade 1) 	
 - Grade 1: treatment with pansoral, talk to

	
 ○ - Moderate and limits activities of daily living (Grade 2) ○ - Severe + Major daily impact 	
 - oncologist at next visit - Grade 2: efferalgan codeine mouthwash for pain. Talk to oncologist at next visit. Alert oncologist by email. - Grade 3: Alert oncologist by email + call oncologist 	
- Fever	
 - Ignition 
 ○ 38-39 °C (Grade 1) ○ 39-40 °C (Grade 2) ○ > 40 °C for less than 24 hours (Grade 3) ○ > 40 °C for more than 24 hours (Grade 4) - Other symptoms? 
 ○ Burning sensation when urinating, cough, diarrhoea, chills, sweats (Grade 1 > 2, Grade 2 > 3) 	
 - No event / prevention: antibiotics not systematically prescribed. - Grade 1: monitor. Paracetamol if <38.2 °C without symptoms / If persistent, change to grade 2 - Grade 2: if 38.2 °C or more after 1h, direct to physician, sign of infection. Alert oncologist by email. - Grade 3: If ~40 °C + sign of an infection, direct to oncologist + alert oncologist by email. - Grade 4: emergency department 	
Other symptoms			
- Headaches	
 - What is the intensity of your headaches? 
 ○ Mild (Grade 1) ○ Moderate (Grade 2): ○ Severe (Grade 3) - Do your headaches impact the activities of your daily life? 
 ○ Does not affect daily life (Grade 1) ○ Makes certain actions difficult to accomplish (Grade 2) ○ Affect activities of daily living (Grade 3) - Presence of dizziness? tinnitus? hypertension or risk of hypertension? (Grade 3) 	
 - Grade 1: treatment with paracetamol (Efferalgan®, Doliprane®) or aspirin (Aspegic®). Reassure the patient as there is no problem of drug interaction. - Grade 2: redirect to general practitioner. Notify during next oncologist visit, particularly if several episodes. - Grade 3: contact oncologist + alert oncologist by email. 	
- Tiredness (asthenia,	
 - What is the intensity of your tiredness? 	
 - Grades 1 and 2: try to maintain a healthy lifestyle 	

apathy, malaise)	
  Mild (Grade 1)  Moderate (Grade 2):  Severe (Grade 3)  Totally incapacitating (Grade 4) 
 - Does your tiredness impact the activities of your daily life? 
  Does not affect daily life (Grade 1)  Makes certain actions difficult to accomplish (Grade 2)  Affects major daily activities (Grade 3) 	
(eat and drink correctly); take as many naps as necessary; exercise a little and relax as much as possible.
 
Stop work during cycle 1 to manage cumulative fatigue over the treatment period
 
 - Grade 3: if persistent tiredness / rapid onset, alert oncologist by email. 	
- Weight loss	
 - Intensity of weight loss 
  5 to 10% of starting weight (Grade 1)  10 to 20% of starting weight (Grade 2)  > 20% of starting weight (Grade 3) 	
 - Grade 1: no care required. Eliminate mucositis, heartburn, dysgeusia. - Grade 2: Implementation of nutritional support by general practitioner. Eliminate mucositis, heartburn, dysgeusia. - Grade 3: Inform oncologist rapidly, requires total secondary nutrition. 	
- Other	cf: CTCAE classification to estimate grade and to determine actions to implement		

D.6. Overview of advice and preventive actions to implement

Instructions: This section is an overview of the advice and preventive actions recommendations that the nurse declares to have given the patient throughout the questionnaire. The purpose of this summary is to underline the actions to implement before ending the call.

Overview of advice given during the interview:

Before finishing, I would like to go over the important points that we spoke of today:

[tick the information issued to the patient and perform a brief recap]

Treatment management advice

- Advice on taking Sutent® (once daily at set times, without opening the capsule. In the event of omission, do not double intake. Observe the physician's decisions in the event of interruption or termination. etc.)
- Advice on using the Sutent® follow-up notebook (treatment calendar, appointment management, adverse event follow-up, etc.)
- Report all adverse events (onset, change or increase, etc.)

General preventive advice:

- Advice on taking systematic preventive treatments (identification of preventive treatments to initiate rapidly)
- Healthy lifestyle advice (healthy eating and drinking, maintaining appropriate physical activity, sleeping and relaxing when necessary, etc.)
- Dietary advice (grapefruit prohibited, healthy and varied diet, etc.)
- Oral hygiene advice (regular mouthwashes, very gently toothbrush, avoid mint-flavoured toothpaste, etc.)

AE-specific preventive advice:

- Prevention of skin toxicity (gentle, fragrance-free soap, hypoallergenic moisturising cream and products, consultation with a chiropodist at the start of treatment, etc.)
- Prevention of digestive disorders (drink sufficiently in small amounts; low-fibre diet; avoid coffee, alcohol, greasy, spicy or acidic food, etc.)
- Prevention of cardiac disorders (frequent blood pressure measurements, limit salt and alcohol intake, etc.)
- Prevention of infectious/inflammatory problems (avoid high-risk contacts, regular hand disinfection, etc.)
- Other preventive advice (fatigue management, pain management, regular appropriate activity, etc.)

Actions recommended to the patient:

- Do not forget the scheduled consultation with the oncologist
- Perform the requested additional examinations (blood pressure monitoring, blood profile, additional examinations requested by the oncologist, etc.)

E. END OF INTERVIEW AND NEW APPOINTMENT

- I would like to thank you for your time and answers.
- As agreed, I would like to propose contacting you again between [theoretical date -1 day] and [theoretical date + 1 day] to go over the management of your treatment and any adverse events. Would you like to make an appointment now?
 - ↳ Yes: agree on an appointment between [theoretical date -1 day] and [theoretical date + 1 day]
 - ↳ No: check the preferred call times
 - ↳ Note any unavailable periods
- Have a nice day.

F. PHARMACOVIGILANCE DECLARATION

Instruction: After finishing the call with the patient, the nurse will be directed to the CATI tool Report section in order to issue any reports of adverse events (new AE or AE follow-up) identified during the call. A new sheet is generated for each AE.

At the end of the call, the sheets are sent to Pfizer's PV department and to the physician via the e-CRF for validation.

G. SUMMARY OF THE INTERVENTION AND ORGANISATION OF PHONE CALLS

Instruction: A summary note will be generated automatically and sent to the physician via the e-CRF. It shall comprise:

- A box with the salient points to be taken into consideration by the physician
- The phone call details (automatic: number of attempts, date and duration of the call)
- A summary of events declared by the patient (new or follow-up)
- Actions undertaken by the patient and actions recommended to the patient.
- Main advice given to the patient

Validation of any discrepancies between patient and e-CRF data will be requested.

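### Biological grade 3/4 events skip the automatic oncologist email, and the Table 8 rows that should cover them fall short for the worst creatinine, platelet and anaemia results

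*Protocol*

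**What the plan says.** Appendix 7 of the protocol is the script for the platform nurses. Section D.5 (New AE collection) sets the automatic rule: "any report of a grade 3 or 4 AE, except for a biological AE, will trigger an email alert for the oncologist". It does not say what a biological event of grade 3 or 4 gets instead.

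Table 8 follows. Each row lists grade limits and, beside them, the actions.

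- Creatinine: the upper grade limits are "Grade 3: 3 to 6* previous value" and then "Grade 4: >10 * previous value". The printed actions end at grade 3, with rapid contact plus email.
- Platelets: the lowest band is grade 3, 25 to 50 x10^9/L, and the last action is "Grade 3: rapidly contact oncologist + alert oncologist by email".
- Anaemia: the two upper actions are "Grade 2: oncologist email alert" and "Grade 3: patient contacts oncologist".
- Neutropenia: both columns run to grade 4, which has its own action (rapid phone contact).

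D.5 also has a separate step for an ongoing grade 3 or 4 event. The nurse marks Yes or No to recommending a pause in sunitinib, and Yes leads to the oncologist being alerted. Biological events are not excluded from this step, and no criterion is given for choosing Yes.

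**The concern.** Laboratory results will reach the nurse. D.3.4 asks patients to have results at hand for the call, and Table 6 codes an abnormal result as an AE. With the automatic email switched off for these events, the Table 8 row is the only place where the script ties a given grade to an obligatory prompt alert. Where a row stops short, a worse result gets less scripted escalation than a milder one.

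What is at stake is how soon the oncologist learns of a severe result. The protocol's own hypothesis (section 8.9, under measurement bias) is that early intervention reduces the most severe events, so a delay at that end of the scale works against the intervention's purpose.

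**Working it through.** No sample size, power or error rate bears on this point. The check compares the grade and action columns of Table 8 and then works out the timing.

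**Rows at the severe end, as printed**

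| Row | Result | Grade | Action |
|---|---|---|---|
| Neutropenia | 0.5 to 1.0 x10^9/L | 3 | email; with fever, also rapid phone contact |
| Neutropenia | below 0.5 x10^9/L | 4 | rapid phone contact |
| Creatinine | 1.5 to 3 times previous | 2 | email |
| Creatinine | 3 to 6 times | 3 | rapid contact plus email |
| Creatinine | 6 to 10 times | none | none |
| Creatinine | above 10 times | 4 | none printed |
| Platelets | 50 to 75 x10^9/L | 2 | email |
| Platelets | 25 to 50 x10^9/L | 3 | rapid contact plus email |
| Platelets | below 25 x10^9/L | no line | none |
| Anaemia | 8 to 10 g/dL | 2 | email |
| Anaemia | below 8 g/dL | 3 | left to the patient |

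The neutropenia row shows that rows were meant to reach grade 4 where that grade can occur, so the creatinine and platelet gaps look like omissions. The creatinine row is split in the text as read, and its missing grade 4 action needs checking against the original. The 6-to-10 gap, the platelet gap and the anaemia inversion do not depend on that check.

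**Timing if no alert is sent**

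Inputs: 6-week cycles with no postponement; calls in weeks 1 to 5 of cycles 1 and 2 and in weeks 2 and 4 of cycles 3 and 4 (Protocol 8.2). Study visits fall at about W6, W12 and W24 (8.2). The script also expects an oncologist visit before cycle 4, at about W18 (Appendix 7, D.2.2.1 and D.3.4).

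Calls therefore fall at study weeks 1 to 5, 7 to 11, 14, 16, 20 and 22.

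Wait to the next expected visit = visit week − call week:
- Cycle 1: 6 − 1 = 5, down to 6 − 5 = 1 week
- Cycle 2: 12 − 7 = 5, down to 12 − 11 = 1 week
- Cycle 3: 18 − 14 = 4 and 18 − 16 = 2 weeks
- Cycle 4: 24 − 20 = 4 and 24 − 22 = 2 weeks

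Gap to the next call:
- Within cycles 1 and 2: 1 week
- Within cycles 3 and 4: 16 − 14 = 2 and 22 − 20 = 2 weeks
- Between cycles: 7 − 5 = 2, 14 − 11 = 3 and 20 − 16 = 4 weeks

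These are upper limits that apply only if every other route fails.

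**The case against.** A reader might infer that prompt alerting of laboratory toxicity depends on Table 8 alone. The documents do not support that. Several other routes remain:

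- the Yes/No recommendation in D.5 to pause sunitinib, which alerts the oncologist and has no biological exemption;
- platform physicians who can assist the nurse if necessary (Protocol 8.2);
- phone contact with the oncologist if necessary (Appendix 7, D.2.1);
- AE sheets and a call summary sent through the e-CRF after the call (Appendix 7, F and G);
- advice at the first call that the patient ring the oncologist or emergency services directly for a serious event (D.2.1).

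This stands, and a careful nurse would probably escalate an extreme result. But none of these is a mandatory prompt alert tied to the grade. The D.5 step has no criterion. It is also keyed to a grade 3 or 4 event, which the printed rows do not assign to creatinine at 6 to 10 times or platelets below 25. It has little use at the week 5 calls, when a patient on the 4-weeks-on, 2-weeks-off regimen is already off the drug. The e-CRF items are passive: section 7.3.1 places the physician's review of nurse-reported events at the follow-up visits. The rest depends on judgement by the nurse or the patient.

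A reader might also count the liver as a gap, because Table 6 lists "Liver profile" and Table 8 has no liver row. That is missing detail rather than a faulty rule. The Other row sends the nurse to the "CTCAE classification to estimate grade and to determine actions to implement". The same row could be used to grade platelets below 25, and Table 7 has a grade 4 box, so the absence of a grade is a fault of the printed row only.

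Finally, grade 3 anaemia does have an action, and the channel can be called a preference. The objection that remains is narrow: the oncologist is emailed at grade 2 but at grade 3 must wait for the patient to call.

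**Conclusion.** The point holds as a minor patient-safety correction. For biological grade 3/4 events, the only grade-specific mandatory prompt alert scripted is the Table 8 row, and the creatinine, platelet and anaemia rows are defective at the severe end. The creatinine grade 4 action is subject to a check of the original layout.

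The delay at risk is at most 5 weeks in cycles 1 and 2 and 4 weeks in cycles 3 and 4. It would usually be shorter, because the summary note and the next call come first. A reader counting only the study visits might infer 24 − 14 = 10 weeks from the first cycle 3 call. D.2.2.1 and D.3.4 treat the first call of each cycle, including cycle 4, as following an oncologist visit, so that figure is not supported.

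How many patients are concerned is unknown. The documents give no rate for creatinine above 6 times the previous value or for platelets below 25 x10^9/L. Protocol 6.1.2 cites 9.3% with grade 3 anaemia, but this does not measure the creatinine and platelet gaps. Nor does it show how many events a nurse would be the first to hear of.

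The primary analysis is unaffected: under section 7.3.1 the physician assigns the definitive grade, whatever the nurse's look-up table says.

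**What to change.** In Table 8:

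- start creatinine grade 4 above 6 times the previous value, and give it at least the grade 3 action (rapid contact plus email);
- add a platelet line below 25 x10^9/L with the same action;
- add an oncologist email to grade 3 anaemia.

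In D.5, add one sentence saying that biological grade 3/4 events are exempt only from the automatic email and follow their Table 8 row. Check the new limits against CTCAE v4.03, which the protocol names as its grading standard.

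The cost is a few cells and a sentence in the nurse script and the CATI system. Oncologists would receive a few more emails, some about tests that they ordered themselves. The sponsor's exemption from the automatic email stays in place.
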